### **Pregnancy statement and use in nursing women**

Azoles can be teratogenic.[57] Information regarding adverse effects on infants of breastfeeding mothers taking azoles is limited. All women of childbearing potential MUST have a negative pregnancy test. If the pregnancy test is positive, the patient must not receive any investigational product and must not be enrolled in the study. We will request that female participants wait 30 days after the last dose of drug before considering becoming pregnant or starting breastfeeding.

**Definition of childbearing potential:** For the purposes of this study, a female of childbearing potential is a sexually mature female who: 1) has not undergone a hysterectomy (the surgical removal of the uterus) or bilateral oophorectomy (the surgical removal of both ovaries) or 2) has not been naturally postmenopausal for at least 24 consecutive months (i.e., has had menses at any time during the preceding 24 consecutive months).

Study participants must be willing to comply with fertility requirements as described below:

- Male participants must agree to use an adequate method of contraception for the duration of the study and for 30 days afterwards.
- Female participants must be either postmenopausal, free from menses  $\geq$  2 yrs, surgically sterilized, willing to use two adequate barrier methods of contraception to prevent pregnancy, or agree to abstain from heterosexual activity starting with screening and for 30 days afterwards.
- Participants must agree not to donate blood, sperm/ova during study participation and for at least 30 days after stopping treatment.

During the course of the trial, if a participant suspects that they may have conceived a child, they will be instructed to contact the study doctor named at the top of this form immediately. In addition, a missed or late menstrual period during the course of the trial should be also reported to the study doctor

If a male patient is suspected of having fathered a child while on study drug, the pregnant female partner must be notified and counseled regarding the risk to the fetus. In addition, the treating physician must follow the course of the pregnancy, including prenatal and neonatal outcome. Infants should be followed for a minimum of 30 days.

Upon live-birth delivery, the minimum information that should be collected includes date of birth, length of pregnancy, sex of infant, major and minor anomalies identified at birth. Outcomes can be obtained via mailed questionnaires, maternal interviews, medical record abstraction, or a combination of these methods.

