## 3.0 Inclusion and Exclusion Criteria

### 3.1 Inclusion Criteria

Patients eligible for enrollment in this study will be male and female adults with a presumed diagnosis of primary or recurrent HGG based on standard of care imaging (contrast-enhanced MRI) and clinical presentation and for whom surgical intervention has been selected as the most appropriate treatment option by the treating physician and patient.

1. Age  $\geq 18$  years
2. Evidence of primary or recurrent HGG that in the opinion of the treating team would require surgical resection
3. Adequate liver function defined as ALT, AST, ALP within 1.5x institutional upper limit of normal (for study drug arm only)
4. Ability to swallow medication (for study drug arm only)
5. Women of child-bearing potential and men must agree to use adequate contraception (hormonal or barrier method of birth control; abstinence) for the duration of study participation (for study drug arm only)
6. Ability to understand and willingness to sign a written informed consent document
7. Be able to comply with treatment plan, study procedures and follow-up examinations

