### 3.2 Exclusion Criteria

1. Patients may not be receiving any other investigational agents while on study
2. Patients who have known allergy to posaconazole or other azoles (for study drug arm only)
3. Patients who have previously had a severe side effect, such as agranulocytosis and neutropenia, in conjunction with previous azole class drugs for a parasitic infection (for study drug arm only)
4. Patients with a history of acute or chronic hepatitis (for study drug arm only)

5. Patients with liver enzymes (ALT, AST, ALP) >1.5x above normal range for the laboratory performing the test (for study drug arm only)
6. Patients who are taking metronidazole and cannot be safely moved to a different antibiotic greater than 7 days prior to starting posaconazole therapy (for study drug arm only)
7. Patients who are taking any anti-convulsant medication that interferes with the cytochrome P450 pathway (e.g. phenytoin, phenobarbital, carbamazepine, etc.) and who cannot be switched to alternative medications such as Keppra (levetiracetam) (for study drug arm only)
8. Uncontrolled intercurrent illness such as chronic hepatitis, acute hepatitis, or psychiatric illness/social situation that would limit compliance with study requirements (for study drug arm only)
9. Patients with a history of Addison's disease or other forms of adrenal insufficiency (for study drug arm only)
10. Patient with little or no stomach acid production (achlorhydria) (for study drug arm only)
11. Pregnant and breastfeeding women
12. Patients with a history of any medical or psychiatric condition or laboratory abnormality that in the opinion of the investigator may increase the risks associated with the study participation or investigational product administration or may interfere with the interpretation of the results.
13. Patients who are not available for follow-up assessments or unable to comply with study requirements
14. Patients who are currently taking medications that induce the metabolism of posaconazole, such as isoniazid, nevirapine, rifamycins (such as rifabutin, rifampin), or St. John's wort and cannot be safely discontinued off of them for the duration of the trial (for study drug arm only).

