#### **4.2.4 Describe the eligibility screening process and indicate whether the screening process will occur before or after obtaining informed consent. Screening begins when the investigator obtains information about or from a prospective participant in order to determine their eligibility. In some studies, these procedures may not take place unless HIPAA Authorization is obtained OR a waiver of HIPAA Authorization when applicable for the screening procedures is approved by the IRB.**

Screening of subjects at is expected prior to obtaining consent to determine potential eligibility.

Once informed consent is obtained, patients will undergo additional screening to determine if they are eligible to participate in the study based on the inclusion/exclusion criteria. If a participant is ineligible for the study drug arm, they will first be considered for candidacy in the ketoconazole study (STUDY00014115). If enrollment in the ketoconazole study is already completed or if the participant is not a candidate for ketoconazole either, then they will be considered for possible candidacy in the control arm of this study.

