All blanks on the consent form, consent addendum forms (if applicable) for subject name, subject initials, dates, signatures, yes/no check boxes for optional research procedures must be completed by the subject themselves if previously approved by the IRB. Delegated research staff will not complete these blanks for the subject.

The PI or delegated research staff will ensure that the subject expresses understanding of information presented on the clinical trial, that participation is voluntary, and that the subject can withdraw at any time without penalty or effects to their medical care. They will ensure that all of the subject's questions have been answered. Participants will also be made aware that by signing the consent form their personal health information and research records may be audited/reviewed by authorized study personnel.

By signing the consent form, the witness attests that the information in the consent form and any other written information was accurately explained to and understood by the subject, and that informed consent was freely given by the subject. The PI or delegated research staff will give a copy of all signed and completed forms to the subject.

The PI will ensure that the subject understands that in order to participate on the clinical trial the subject must be eligible per the protocol's inclusion and exclusion criteria.

The informed consent document will clearly describe the potential risks and benefits of the trial, and each prospective participant must be given adequate time to discuss the trial with the PI or delegated staff and to decide whether or not to participate. The informed consent will be approved by the IRB prior to being presented to a potential patient.

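### The drug-arm contraception criterion in section 3.1 is looser than the mandatory fertility rule in section 10.0, and the protocol does not say which one governs

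*Combined protocol and SAP*

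**What the plan says.** Section 3.1, inclusion 5, applies to the study drug arm. Its accepted methods and period are "hormonal or barrier method of birth control; abstinence) for the duration of study participation". It covers men and women of childbearing potential, and one method is enough.

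Section 10.0, under the pregnancy and nursing statement, opens with "Study participants must be willing to comply with fertility requirements as described below". A female participant must be postmenopausal, surgically sterilized, "willing to use two adequate barrier methods of contraception to prevent pregnancy", or abstinent from screening until 30 days afterwards. For men the text is "Male participants must agree to use an adequate method of contraception for the duration of the study and for 30 days afterwards". The same statement asks that "female participants wait 30 days after the last dose of drug before considering becoming pregnant". It defines childbearing potential so that only hysterectomy, bilateral oophorectomy or 24 months of natural menopause removes a woman from the category.

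On entry, section 4.2.4 describes "additional screening to determine if they are eligible to participate in the study based on the inclusion/exclusion criteria", and section 5.2 has the investigator explain that "the subject must be eligible per the protocol's inclusion and exclusion criteria". Neither mentions section 10.0.

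On pregnancy testing, section 7.2.1 and the first footnote to the schedule of events accept a result from the 31 days before consent or screening. The schedule shows a test at Visit 1 only.

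**The concern.** Two rules on the same matter sit in one protocol, both are binding in tone, and they differ on method and on duration. Staff working from the section 3 checklist would admit a woman using hormonal contraception alone. Section 10.0 would then make her non-compliant from her first dose.

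What is at stake is participant safety and consistent eligibility decisions. The protocol itself says that azoles can be teratogenic and can cause birth defects. The method difference matters more than the duration difference, because it applies while drug is being taken.

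**Working it through.** The plan gives no figure to reproduce here. The check is a comparison of the two rules and some day counts.

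**Rules compared (drug arm)**

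| Participant | Inclusion 5 | Section 10.0 |
|---|---|---|
| Woman, hormonal method only | passes | fails: not listed |
| Woman, one barrier method | passes | fails: two required |
| Abstinent woman who stops at study end | passes | fails, if the 30 days run beyond study end |
| Man who stops at study end | passes | fails: 30 more days required |
| Woman sterilized other than by hysterectomy or bilateral oophorectomy, not menopausal, no contraception | fails, if the section 10.0 definition applies | passes as surgically sterilized |
| Woman on two barrier methods, or abstinent, for the longer period | passes | passes |

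The last row shows that both rules can be met together. The row above it shows that section 10.0 is not the stricter rule in every case.

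**Duration.** Inputs: the last dose is on the morning of postoperative day 1 (section 7.2.5), and participation ends at the 14 ± 7 day follow-up, so on day 7 to 21 (sections 7.2.7 and 8.3).

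- Thirty days after the last dose: 1 + 30 = day 31.
- Shortfall of inclusion 5: 31 − 21 = 10 days to 31 − 7 = 24 days.
- Men's rule in section 10.0: 7 + 30 = day 37 to 21 + 30 = day 51, which is 6 to 20 days later than day 31.
- For women, the start of the 30 days is not stated, and the phrase may attach only to abstinence.

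**Dosing window in which the method difference applies.**

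- Section 7.2.1: 168–240 h before surgery = 7–10 days, plus 1 day to the last dose = 8–11 days.
- Section 7.4.6.3: 130–155 h = 5.4–6.5 days, plus 1 day = 6.4–7.5 days.

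**Drug left when inclusion 5 ends.** The fraction remaining is 2^(−h/t½), assuming simple first-order decline after the last dose, with half-lives of 15–35 h (section 7.4.1).

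- Day 7 (144 h): 0.13% to 5.8%.
- Day 14 (312 h): at most 0.21%.
- Day 21 (480 h): at most 0.007%.

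**Age of an accepted pregnancy test at first dose.** Assume the oldest permitted result (31 days), consent at Visit 1, and surgery 7–10 days after Visit 1.

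- Section 7.2.1: first dose 0 to 3 days after Visit 1 (at the latest, 10 − 7 = 3), so 31 to 34 days.
- Section 7.4.6.3: first dose 7 − 6.46 = 0.5 to 10 − 5.42 = 4.6 days after Visit 1, so about 31.5 to 35.6 days.

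**The case against.** The strongest reply is that the rules are cumulative: inclusion 5 sets a minimum for entry and section 10.0 adds what participants must then do. General compliance clauses point the same way. Exclusion 13 removes "Patients who are not available for follow-up assessments or unable to comply with study requirements", inclusion 7 requires ability to comply with study procedures, and section 3.3.1 allows withdrawal for not adhering to the protocol. This is a reasonable reading, and it rules out the claim that nobody can satisfy both rules. But none of these clauses names contraception or refers to section 10.0, so they do not tell staff which list of methods to apply.

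There are also real safeguards. Pregnancy is an exclusion, a screen failure and a reason to stop therapy. The study doctor discusses methods, late periods are to be reported, and drug is withheld if pregnancy is suspected (section 18.2). They lower the risk, but most act on a known or suspected pregnancy, and none says which methods are acceptable.

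A reader might infer that section 10.0 also binds control participants, since its opening sentence has no arm limit. That is weak: the surrounding text speaks of the last dose and of stopping treatment, which mean nothing for people who receive no drug. It is a reason to state the arm, not a separate fault.

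The age of the pregnancy test contradicts nothing in the protocol, and its figures are worst cases. It is a separate improvement and adds no weight to the mismatch.

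**Conclusion.** The mismatch holds. Inclusion 5 is looser than section 10.0 on method for women and on duration for both sexes, and no text says which governs. Inclusion 5 ends 10 to 24 days before 30 days after the last dose.

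A reader might infer that the two rules are incompatible, or that section 10.0 is simply the stricter one. The documents support neither: both can be met together, and the treatment of surgical sterilization runs the other way.

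The practical size is modest. The method difference reaches only non-abstinent women of childbearing potential in the drug arm, over roughly 6 to 11 days of dosing. The duration difference reaches men and women but is pharmacologically minor, with at most about 6% of drug left by day 7 under the assumptions above. The plan does not say how many such participants to expect; among five evaluable drug-arm patients plus replacements, the number may be small or zero. The AUC analysis and the success criteria are unaffected. It should still be corrected, because the change is cheap and the protocol calls the drug class potentially teratogenic.

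**What to change.** Put one rule for the drug arm, in identical words, in section 3.1 and section 10.0, and check the consent form against it. The rule should contain:

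- one list of methods chosen by the clinical team, stating whether hormonal contraception or a single barrier method is enough;
- how surgical sterilization is treated, consistent with the definition of childbearing potential;
- a duration of at least 30 days after the last dose for both sexes. Men's cover now runs to day 37–51; if it is shortened towards day 31, say so and justify it.

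Separately, exempt the pregnancy test from the 31-day look-back in section 7.2.1 and the schedule footnote, and require a negative result at Visit 1 before posaconazole is dispensed.

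The cost is wording, plus at most one extra test per woman of childbearing potential in the drug arm. Drug-arm participants already give blood at Visit 1 and wait for results, usually within 4 hours.

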### **Risk of loss of confidentiality**

There is a risk of loss of confidentiality if participant information or identity is obtained by someone other than the investigators, but precautions will be taken to prevent this from happening. The confidentiality of participant electronic data created by the participant or by the researchers will be maintained as required by applicable law and to the degree permitted by the technology used. Absolute confidentiality cannot be guaranteed.

## **11.0 Potential Benefits to Subjects and Others**

### **11.1 Potential Benefits to Subjects**

There will be no direct benefit to study participants.

### **11.2 Potential Benefits to Others**

The use of posaconazole as a drug against HGGs has never been formally studied and this is a unique opportunity to study this possible indication. If posaconazole successfully demonstrates effective accumulation in brain and tumor interstitium and result in the expected pharmacodynamics changes, it could be of major importance in improving the outcome of patients with HGGs.

## **12.0 Sharing Results with Subjects**

If the research with the participants identifiable information or samples gives results that do have meaning for their health, the researchers will contact the participants to let them know the findings and discuss the potential implications with them.

## **13.0 Subject Payment and/or Travel Reimbursements**

Participants will receive a \$50.00 gift card (via Greenphire) for completing the research-only visit (Visit 2) if it is performed. No compensation will be provided for any other study visits.

## **14.0 Economic Burden to Subjects**

### **14.1 Costs**

There will be no additional costs to the participants for enrolling on the trial.

- The study drug, posaconazole, will be provided at no cost to the study drug group participants while they take part in this study.
- The research-related tests and procedures that will be provided at no cost to the participants include:
  - CMP at Visits 1, 2, and 5, including blood draws (study drug group only)
  - 12-lead ECG at Visit 2 (study drug group)
  - Physical examination at Visit 2 (study drug group)
  - Microdialysis catheter and related reagents, and catheter monitoring at visits 3 through 6 both groups)
  - The removal of the microdialysis catheter will also be at no charge, performed at the bedside (both groups)

### **14.2 Compensation for research-related injury**

It is the policy of the institution to provide neither financial compensation nor free medical treatment for research-related injury. In the event of injury resulting from this research, medical treatment is available but will be provided at the usual charge. Costs for the treatment of research-related injuries will be charged to subjects or their insurance carriers.

## **15.0 Resources Available**

### **15.1 Facilities and locations**

The study will be conducted in the Neurosurgery Clinic, operating room (collection of samples, placement of MDCs), and in post-operative rooms in the hospital at the Penn State Hershey Medical Center.

### **15.2 Feasibility of recruiting the required number of subjects**

The clinical investigators are involved in the care of any patient diagnosed with glioblastoma. Not all will be appropriate study candidates, but the likelihood of identifying and recruiting 10 subjects is high.

### **15.3 PI Time devoted to conducting the research**

The PI and other clinical co-investigators will screen and identify appropriate subjects as part of their routine clinical activity of caring for patients. The clinical investigators are supported by a team of clinical research staff who will assist in the completion of the research procedures. All clinical members of the research team are experienced clinicians and researchers, who have successfully balanced their clinical and research responsibilities.

#### 15.4 Availability of medical or psychological resources

All resources and facilities of the HMC are available to subjects on study, as part of their routine standard of care. No additional resources are anticipated to be needed specifically due to participation in this study.

#### 15.5 Process for informing Study Team

Members of the research team will be required to undergo protocol training and to sign a delegation of duties log prior to participation in the study. During the study, the PI and/or study coordinator will communicate updates to all team members as they become aware of any changes or updates.

### 16.0 Other Approvals

#### 16.1 Other Approvals from External Entities

Will need approval from grant funders.

#### 16.2 Internal PSU Committee Approvals

**Check all that apply:**

- Anatomic Pathology – Penn State Health only** – Research involves the collection of tissues or use of pathologic specimens. Upload a copy of “HRP-902 - Human Tissue For Research Form” in CATS IRB.
- Animal Care and Use – All campuses** – Human research involves animals and humans or the use of human tissues in animals
- Biosafety – All campuses** – Research involves biohazardous materials (human biological specimens in a PSU research lab, biological toxins, carcinogens, infectious agents, recombinant viruses or DNA or gene therapy).
- Clinical Laboratories – Penn State Health only** – Collection, processing and/or storage of extra tubes of body fluid specimens for research purposes by the Clinical Laboratories; and/or use of body fluids that had been collected for clinical purposes but are no longer needed for clinical use. Upload a copy of “HRP-901 - Human Body Fluids for Research Form” in CATS IRB.
- Clinical Research Center (CRC) Advisory Committee – All campuses** – Research involves the use of CRC services in any way.
- Conflict of Interest Review – All campuses** – Research has one or more of study team members indicated as having a financial interest.
- Radiation Safety – Penn State Health only** – Research involves research-related radiation procedures. All research involving radiation procedures (standard of care and/or research-related) must upload a copy of “HRP-903 - Radiation Review Form” in CATS IRB.
- IND/IDE Audit – All campuses** – Research in which the PSU researcher holds the IND or IDE or intends to hold the IND or IDE.
- Scientific Review – Penn State Health only** – All investigator-written research studies requiring review by the convened IRB must provide documentation of scientific review with the IRB submission. The scientific review requirement may be fulfilled by one of the following: (1) external peer-review process; (2) department/institute scientific review committee; or (3) scientific review by the Clinical Research Center Advisory committee. NOTE: Review by the Penn State Health Cancer

Institute (PSCI) Protocol Review Committee or the PSCI Disease Team is required if the study involves cancer prevention studies or cancer patients, records and/or tissues. For more information about this requirement see the IRB website.

